**Aim 3: Comparison of inflammatory response: systemic and pericardial between patients who received AM and controls**

The proinflammatory response to cardiopulmonary bypass circuit as measured by numerous systemic and pericardial inflammatory markers i.e. C-reactive protein (CRP), TNF- $\alpha$ , Interleukin (IL)-6 and brain natriuretic peptide (BNP), have been linked to induction of atrial fibrillation in a number of previous publications. Hence, these markers were chosen for our study purposes. We will collect pericardial (from chest tubes) and systemic fluid markers at pre-specified intervals. We will assess the percentage change in the levels of the biomarkers as compared to their pre-operative baseline as there will be expected variability in the level of these biomarkers at baseline.

We have assembled a strong team that combines the expertise and resources of CellReGen, the clinical knowledge of the Divisions of Cardiothoracic Surgery and Cardiovascular Medicine, and the translational depth of the Cardiovascular Research and Training Institute (CVRTI). We expect that this focused clinical trial will provide the necessary data to expand the use of AM in a large scale, extra-murally funded multi-institutional trial.

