### **Research Design and Methods**

All patients enrolled in the study will undergo the standard procedures as part of the surgical preparation and follow-up. The study is comprised of five main time periods: 1) Pre-operative screening 2) manufacturing and storage of hAM, 3) surgical application/implantation with hAM, 4) follow up and evaluation of postoperative efficacy of hAM, 5) collection and analysis of clinical data.

**Preoperative screening** We will enroll 40 patients undergoing elective coronary artery bypass grafting (CABG). The successfully screened cohort will be randomized to (20 patients in each arm): Interventional arm (patients who will have AM placed epicardially) and control arm (pericardial closure over great vessels and base of right ventricle, leaving the bottom part uncovered).

A pre-surgical echocardiogram will be conducted to evaluate ejection fraction, valvular dysfunction, cardiomyopathy, chamber dimensions, cardiac motion, and strain. Candidate predictor variables (patients' demographic features and clinical risk factors), echocardiographic parameters like atrial dimensions and ejection fraction, CHA2DS2-VASc score, and other patient factors will be collected.

**Inclusion Criteria:** Patients undergoing primary elective CABG at the University of Utah Hospital; Patients 18 years or older; Ability to provide informed consent and follow-up with protocol procedures

**Pre-operative Exclusion Criteria:** Patients in AF at the time of surgery; Prior history of sternotomy; Prior history of pericarditis; Currently on aggressive antiarrhythmic therapy (does not include beta blockers); Patients with an implantable cardiac device (pacemaker, ICD, CRT-D), ejection fraction <45%.

Patients will be randomly assigned 1:1 to the control group or the study treatment group through a computer system, REDCap, to eliminate biased treatment assignments.

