**Manufacturing and storage of AM:** Amnion is processed from placenta that is procured from volunteer donors according to protocols approved by the Institutional Review Board at the University of Utah. The birth tissue is placed into a sterile plastic receptacle that contains 0.9% Sodium Chloride and is transported to CellReGen for processing. The amniotic membrane is carefully separated from the chorion using blunt finger dissection. Two 2x2 cm^2 sections are cut from the amnion for sterility testing. The amnion is sent for gamma irradiation. After return of the irradiated amnion, an inspection of the product is made and the packaged membrane is stored in quarantine until the donor's medical and donor screening answers and their infectious disease testing results are reviewed and signed-off by the Medical Director, QA Specialist and Scientific Director. The customized 7x15 cm sized, rectangular shaped GMP-grade wet AM placed on Telfa gauze will be provided inside the foil pouch for this clinical trial.

**Surgical application/implantation of AM:** The packaged wet AM placed on Telfa gauze inside of a foil pouch, will be transferred from CellReGen to the OR. At the end of planned cardiac surgery, the size and shape of customized 7x15 cm AM can be easily adjusted according to the size of the pericardium defect.

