## Follow-up Evaluation

### a. Collection of inflammatory markers

The systemic and pericardial inflammatory markers, e.g., C-reactive protein (CRP), TNF- $\alpha$ , Interleukin (IL)-6 and brain natriuretic peptide (BNP), will be collected at the time of pericardiectomy. Pericardial fluid during surgery will be suctioned into a Luken trap directly from the pericardial sac. Postoperatively, the pericardial markers will be collected from the mediastinal chest tube drainage. The inflammatory markers will be collected at 24 hours, 48 hours, and 72 hours post-closing. These markers will be analyzed through ARUP.

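### Aim 3's post-operative 'pericardial' markers come from mediastinal drainage but their only baseline is pericardial sac fluid, so percentage change compares two different fluids

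*Combined protocol and SAP*

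**What the plan says.** All places are in the Combined protocol and SAP.

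- **Baseline fluid** (Follow-up Evaluation, a. Collection of inflammatory markers): "Pericardial fluid during surgery will be suctioned into a Luken trap directly from the pericardial sac".
- **Post-operative fluid and times** (same section): "Postoperatively, the pericardial markers will be collected from the mediastinal chest tube drainage", and "The inflammatory markers will be collected at 24 hours, 48 hours, and 72 hours post-closing".
- **Label** (Specific Aims, Aim 3): "We will collect pericardial (from chest tubes) and systemic fluid markers at pre-specified intervals".
- **Endpoint** (Aim 3): "We will assess the percentage change in the levels of the biomarkers as compared to their pre-operative baseline". The reason given is that baseline levels are expected to vary between patients.
- **What differs by arm** (Research Design and Methods): controls have "pericardial closure over great vessels and base of right ventricle, leaving the bottom part uncovered". In the other arm the membrane is applied to the epicardium, and its size and shape "can be easily adjusted according to the size of the pericardium defect".
- **Analysis and decision** (Statistical Methods; Sample Size Justification): continuous outcomes are compared by a two-sample t-test. A trend favouring AM is enough to support the next study, and significance is not required.

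**The concern.** There are two separate issues.

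**Change of fluid.** The sac sample is pericardial fluid. Mediastinal drainage may also contain blood and exudate from the surgical wound. A percentage change from the first to the second mixes any change in inflammation with the change in what was sampled. This affects both arms. By itself it harms interpretation and does not bias the comparison between arms.

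**Possible difference by arm.** The arms differ in what lies over the lower part of the heart. If the membrane alters how much pericardial fluid or mediastinal blood reaches the drain, the drainage level could differ by arm with identical inflammation. Such a difference would follow from the intervention, so randomisation would not remove it. The argument in Statistical Methods that randomisation makes simple tests sufficient addresses confounding, not a measurement that differs by arm.

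At stake is the claim about local inflammation. The bar for a positive signal is only a trend in the expected direction.

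**Working it through.** **The plan's own figure.** Sample Size Justification gives 80% power for a 0.80 SD difference, 20 per group, two-sided alpha 0.10. The noncentrality is 0.80 × √(20/2) = 2.530. The noncentral t with 38 df gives 79.9%; the normal approximation gives Φ(2.530 − 1.645) = 81.2%. The figure reproduces and is not in dispute.

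**Which sample is the baseline?** Aim 3 calls it pre-operative. The collection section lists one pericardial sample before the drainage samples, the intra-operative sac fluid. The plan does not say in so many words that this is the denominator for drainage, but it collects no other pericardial baseline.

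**Assumed mixing model.** Let f be the pericardial share of the drainage and k the ratio of the pericardial to the mediastinal level. In units of the mediastinal level,

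drainage = f·k + (1 − f).

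The documents give neither f nor k. Background and Significance reports a 4 to 700-fold increase for a list of factors, but its comparator is unclear, and of the four Aim 3 markers (CRP, TNF-α, IL-6, BNP) only TNF-α is on that list. I therefore also show k of 0.5, 1 and 2.

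*Step 1: the change of fluid alone.* Suppose the pericardial level has not moved from the sac baseline. Then drainage/baseline = f + (1 − f)/k. With f = 0.5 and k = 4 this is 0.5 + 0.125 = 0.625, an apparent change of −37.5%.

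*Step 2: a difference by arm.* Give both arms the same k and the same baseline, and let only f differ. The AM/control ratio is (f_AM·k + 1 − f_AM)/(f_C·k + 1 − f_C). With k = 4, f_C = 0.50 and f_AM = 0.25 it is 1.75/2.50 = 0.70.

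| k | Step 1: apparent change, f = 0.5 | Step 2: f 0.50 control, 0.40 AM | f 0.50 control, 0.25 AM | f 0.40 control, 0.50 AM |
|---|---|---|---|---|
| 0.5 | +50% | 1.07 | 1.17 | 0.94 |
| 1 | 0% | 1.00 | 1.00 | 1.00 |
| 2 | −25% | 0.93 | 0.83 | 1.07 |
| 4 | −37.5% | 0.88 | 0.70 | 1.14 |
| 700 | −49.9% | 0.80 | 0.50 | 1.25 |

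Equal shares, or k = 1, give no difference by arm. Otherwise the ratio can fall on either side of 1.

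*Step 3: what a spurious shift would do to one comparison.* With 20 per arm and a shift of d SD towards AM, the chance of the expected direction is about Φ(d√10). The chance of p < 0.10 favouring AM is from the noncentral t.

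| Spurious shift towards AM (SD) | Expected direction | p < 0.10 favouring AM |
|---|---|---|
| 0 | 50% | 5% |
| 0.2 | 74% | 15% |
| 0.4 | 90% | 34% |
| 0.8 | 99% | 80% |

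A shift the other way would hide a real benefit to the same degree.

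**Does dividing by the sac level help with baseline variability?** On the log scale, if both fluids have SD σ and correlation ρ, the change has variance 2(1 − ρ)σ², against σ² for the drainage level alone. The change is the noisier measure whenever ρ < 0.5. The plan gives no value for ρ across two fluids. Using the sac level as a covariate lets the data decide how much it contributes.

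**The case against.** A reader might infer that the membrane closes the pericardial opening in one arm and that the bias therefore favours AM. The documents do not support that.

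- **No seal is described.** The membrane goes on the epicardium and can be trimmed to the defect. Fixation and fluid-tightness are not mentioned. Strengths and Limitations calls existing substitutes structural barriers, but that describes other products.
- **Tube position is not given.** Aim 3's label suggests the authors expect the tubes to drain the pericardial space. If every tip lay on the pericardial side in both arms, the mechanism for a difference by arm would largely go.
- **Direction is open.** A membrane that keeps mediastinal blood out of the sample would raise the AM reading when k exceeds 1 (1.14 to 1.25 in the last column for k of 4 to 700). A marker with k below 1 also reverses the sign.
- **Step 3 is conditional.** It says what a given shift would do, not that one exists. It uses a t-test on a generic scale, not the planned percentage change.
- **Reach is limited.** The trend criterion covers Aims 2 and 3 together. POAF and the systemic markers are unaffected, and safety is the primary objective.

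All of this stands, and it rules out a claim of established bias. It does not answer the change of fluid, which is explicit in the collection section and resolved nowhere else. Nor does it exclude a difference by arm, because the plan neither fixes nor records what would settle it.

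**Conclusion.** The point holds in two parts of unequal strength.

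**Established from the text:** the pericardial percentage change in Aim 3 has sac fluid in the denominator and mediastinal drainage in the numerator. It is hard to interpret in both arms. This rests on one inference, that the sac sample is the pericardial baseline, and the plan offers no alternative.

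**Possible but not established:** a difference by arm in what the drain collects. The ratios of 0.50 to 1.25 depend wholly on assumed shares and concentration ratios. They show that the effect could matter, not that it is present or that it favours AM.

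This is worth correcting because Aim 3 feeds the case for a larger trial on a low bar. It does not invalidate the trial or Aim 3 as a whole.

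**What to change.** 1. **Aim 3 and Collection of inflammatory markers:** call the post-operative sample mediastinal drainage, and do not compute percentage change from the sac sample for it.
2. **Analysis:** compare the arms on post-operative drainage levels, for example on the log scale, with the sac level as a covariate if wanted. Keep change from baseline for the systemic markers, where the fluid is the same.
3. **Case report form:** record in both arms whether the tube tip lies inside or outside the pericardium or membrane. This is best noted at operation, so the field should exist before enrolment. Tabulate it by arm; splitting 20 per arm by it would add little. This asks for a record, not a change in tube placement.
4. **Statistical Methods:** state that a drainage difference is not by itself evidence of lower pericardial inflammation unless tubes were on the pericardial side in both arms, and that it will be read alongside the systemic markers.

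The cost is wording in three places and one form field, with no extra sample, assay or patient. The downside is a weaker claim about local inflammation, which is the mechanism that motivates the trial.

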### b. Monitoring of POAF (Time frame: from discharge through surgical follow-up appointment)

The incidence of POAF would be quantified for the period between the patient's discharge and their return to clinic for the surgical post-operative follow-up appointment. Patients will be on continuous telemetry while in the hospital. They will be discharged home with a KardiaMobile EKG device, and asked to record a 6-lead EKG once daily during this period between discharge and their follow-up appointments. The number of occurrences and duration of any POAF episodes (atrial fibrillation burden) will be recorded and treated according to standard clinical practices.

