**Aim 2: Compare incidence of POAF for until post-operative follow-up**

The incidence and burden of POAF will be assessed using 24 hour telemetry during hospital stay as well as a daily EKG reading at home between discharge and post-operative follow-up appointment.

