### c. Procedure-related serious adverse events [Time Frame: through post-operative follow-up]

Case-report forms will include collection of data for adverse events including, but not limited to, mortality, myocardial infarction, tamponade, bleeding, deep wound infection, stroke, and pericarditis. While patients will not be required to receive a post-operative echocardiogram, those who do for standard of care purposes will have that data collected in the CRF.

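### Aim 2 counts post-operative AF from the hospital stay onward, but the monitoring section starts the incidence count at discharge

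*Combined protocol and SAP*

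**What the plan says.** Two parts of the combined protocol and SAP set a window for the same outcome.

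- **Specific Aims, Aim 2.** "The incidence and burden of POAF will be assessed using 24 hour telemetry during hospital stay". To this the aim adds one home EKG per day until the patient is seen at follow-up. The window covers the hospital stay and the time at home up to the follow-up visit.
- **Follow-up Evaluation, section b.** The heading is "Monitoring of POAF (Time frame: from discharge through surgical follow-up appointment". The first sentence quantifies incidence between "discharge and their return to clinic for the surgical post-operative follow-up appointment". This is the same interval in which patients are asked to "record a 6-lead EKG once daily during this period between discharge and their follow-up appointments".

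Section b also says "Patients will be on continuous telemetry while in the hospital", and that "The number of occurrences and duration of any POAF episodes" will be recorded. Neither statement says that inpatient episodes count toward incidence.

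Statistical Methods gives the test for binary outcomes (chi-square or Fisher's exact) but no POAF window. The next heading, section c, reads "Procedure-related serious adverse events [Time Frame: through post-operative follow-up" and has no discharge start.

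**The concern.** One window includes the hospital stay and the other excludes it. If an analyst followed section b as written, three things would go wrong.

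1. A patient with AF in hospital that resolves before discharge would be counted as POAF-free. Background and Significance says that POAF often occurs in the first week after surgery.
2. The count would drop the period of continuous monitoring and rest on one EKG a day.
3. The count would start at a time that the outcome itself can move. Background and Significance says POAF adds 2 to 5 hospital days.

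The POAF rate has two uses in Statistical Methods: the judgement that a trend in the expected direction supports a larger study, and the descriptive figures for sizing that study. With two windows available, the rate could be the wrong one, or could be chosen after the data are seen.

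**Working it through.** **The plan's own figures.** The only power figure for the efficacy aims is 80% for a 0.80 SD difference in means with 20 per group at two-sided alpha 0.10. The noncentrality is 0.80 × √(20/2) = 2.53 on 38 degrees of freedom, which gives 79.9%, so the figure reproduces. It concerns a continuous outcome and does not depend on the POAF window. No power is stated for POAF incidence.

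**The texts side by side.**

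| Place | Start | End | Source of data |
|---|---|---|---|
| Aim 2 | Hospital stay | Follow-up visit | Telemetry and home EKG |
| Section b, heading | Discharge | Follow-up visit | Not stated |
| Section b, first sentence | Discharge | Follow-up visit | Not stated |
| Statistical Methods | Not stated | Not stated | Not stated |

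The discharge start appears twice in section b. No other section says which window governs.

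**Illustration of what the window could do.**

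Inputs from the documents:
- 20 patients per arm (Preoperative screening).
- POAF in 20% to 50% of patients (Background and Significance). I use control rates c = 20%, 30% and 50%.

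Assumptions not in the documents:
- AM halves POAF, equally before and after discharge.
- A share k of POAF patients is counted, the same in both arms. k = 1 is the full window; 0.5 and 0.1 are trial values for a count that starts at discharge.
- The yardstick is strictly fewer POAF patients in the AM arm. The plan does not define its trend.

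Formula: X ~ Binomial(20, k·c/2) in the AM arm and Y ~ Binomial(20, k·c) in the control arm, independent. P(X < Y), P(X = Y) and P(X > Y) come from summing the joint probabilities exactly. Expected control events are 20·k·c; for example, 20 × 0.1 × 0.30 = 0.6.

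| k | c | Expected control events | AM fewer | Tie | AM more |
|---|---|---|---|---|---|
| 1 | 20% | 4 | 0.750 | 0.121 | 0.128 |
| 1 | 30% | 6 | 0.833 | 0.079 | 0.088 |
| 1 | 50% | 10 | 0.935 | 0.033 | 0.033 |
| 0.5 | 20% | 2 | 0.614 | 0.212 | 0.174 |
| 0.5 | 30% | 3 | 0.693 | 0.155 | 0.152 |
| 0.5 | 50% | 5 | 0.796 | 0.097 | 0.107 |
| 0.1 | 20% | 0.4 | 0.282 | 0.592 | 0.126 |
| 0.1 | 30% | 0.6 | 0.365 | 0.481 | 0.154 |
| 0.1 | 50% | 1.0 | 0.474 | 0.348 | 0.178 |

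At k = 0.1 the chance of no POAF patient in either arm is 0.546, 0.402 and 0.216 for the three control rates. Much of the lost signal therefore becomes ties rather than results in the wrong direction.

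**The case against.** The best defence is that the intent can be inferred. Aim 2 states the outcome and includes inpatient telemetry. The Specific Aims speak of POAF after cardiac surgery, not after discharge. Section b itself provides for telemetry and for the duration of any episode, and one EKG a day cannot measure duration. The discharge start then looks like loose drafting in a section about follow-up. The defence adds that nothing is lost at source, that POAF is secondary to safety, and that the plan asks only for a trend.

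Most of this stands. It shows which window was probably meant and keeps the consequence modest. It does not remove the conflict, because the only sentence in section b that says when incidence is quantified starts at discharge.

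The objections to the illustration also stand:
- The halving and the counted shares are assumptions, so the table shows sensitivity and not the actual loss.
- At 20% control POAF, the chance of a wrong-direction result is about the same at k = 0.1 (12.6%) as over the full window (12.8%).
- The model holds k equal between arms, so it does not test whether delayed discharge biases the comparison.
- The heading of section c names no start at all, so it is weak evidence that the discharge start in section b was deliberate.

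**Conclusion.** The contradiction holds: the two sections give different incidence windows for the same outcome and nothing reconciles them. It should be fixed. It concerns the definition of a secondary outcome, not data capture, and no safety conclusion depends on it.

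The size of the loss cannot be computed, because the documents give neither the share of POAF confined to the hospital stay nor the AM effect. Under the stated assumptions, the chance of fewer POAF patients in the AM arm falls from 75–93% over the full window to 61–80% if half of POAF patients are counted and 28–47% if a tenth are. The ranges span control rates of 20% to 50%. The finding itself rests on the wording and needs none of these assumptions.

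**What to change.** Reword the heading and first sentence of section b so that the window matches Aim 2. For example: *Time frame: end of surgery through the surgical follow-up appointment. POAF incidence is any AF in this period, detected by inpatient telemetry or home EKG.* Aim 2 gives neither an exact start event nor a case definition, so the sponsor should confirm both parts of that example. Name the same window for the POAF comparison in Statistical Methods. AF after discharge can be reported separately as a descriptive result.

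The cost is one heading, one sentence and a short cross-reference. Telemetry and home EKGs are already planned, so no recording or visit is added. The change is best made before outcome data are examined.

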## Specific Aims

Cardiopulmonary bypass triggers a systemic and localized inflammatory response which has been shown to serve as a trigger for POAF onset. Some evidence further suggests that releasing the heart from its natural pericardial restraint can augment this response.

The Cell Therapy and Regenerative Medicine Program (CellReGen) at the University of Utah manufactures sterile AM for human use which is currently used to enhance wound healing, particularly in burn patients. Early investigation by our basic science laboratory has demonstrated that placement of AM on rat hearts after myocardial infarction can decrease myocardial scarring.

The primary objective of this research endeavor is to determine the safety of AM as a pericardial substitute in cardiac surgery with a secondary aim as to whether application of AM decrease the incidence of POAF following cardiac surgery. We hypothesize that application of AM at the time of cardiac surgery will decrease inflammation and the subsequent substrate for the development of POAF. In order to test this hypothesis, we

propose a pilot clinical trial in patients undergoing cardiac surgery at the University of Utah with the following specific aims:

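### The monitoring section starts the POAF incidence window at discharge, against Aim 2, and a once-daily home EKG cannot supply the episode count and duration that define burden

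*Combined protocol and SAP*

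**What the plan says.** The Specific Aims section gives the efficacy question as a "secondary aim as to whether application of AM decrease the incidence of POAF following cardiac surgery". Aim 2 then names two measures and two sources. For the inpatient period it says "The incidence and burden of POAF will be assessed using 24 hour telemetry during hospital stay". For the time after discharge it adds a second source to the same sentence: "as well as a daily EKG reading at home between discharge and post-operative follow-up appointment". Its heading gives an end to the window (post-operative follow-up) but no start.

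Follow-up Evaluation, section b, is narrower. Its heading carries "Time frame: from discharge through surgical follow-up appointment", and its first sentence says "The incidence of POAF would be quantified for the period between the patient's discharge and their return to clinic". It then describes two kinds of rhythm data:

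- in hospital: "Patients will be on continuous telemetry while in the hospital";
- at home: patients are "asked to record a 6-lead EKG once daily during this period".

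It closes with "The number of occurrences and duration of any POAF episodes (atrial fibrillation burden) will be recorded", without naming the source of those data.

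Statistical Methods compares binary outcomes by chi-square or Fisher's exact test and continuous outcomes by a two-sample t-test. A trend in the expected direction would support a larger study, and the descriptive statistics are to inform that study's sample size. The plan does not define an AF episode, set a minimum duration, or say how single tracings become episodes.

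**The concern.** There are two separate problems in one short section.

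**Window.** Incidence is the stated secondary aim. Section b and Aim 2 give different rules for who counts as a case. A patient with AF on telemetry on day 3 and sinus rhythm at home is a case under Aim 2 and not under section b. The Background places POAF often in the first week after surgery, so the narrower rule may omit much of the outcome that the trial wants to compare.

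**Burden.** Section b defines burden as episode count and duration, and Aim 2 lists the home EKG among the sources for burden. Read together, they assign to a daily spot tracing a quantity that it cannot show. Any post-discharge count or duration would then rest on an unstated conversion rule. Its mean and SD would enter the t-test, the judgement of trend and the planning of the next study.

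**Working it through.** **1. The plan's own figure.** The plan gives no figure for POAF detection, count or duration. The nearest is 80% power for a 0.80 SD difference with 20 per group at two-sided alpha 0.10. The noncentrality is 0.80/√(2/20) = 2.53 on 38 df, and exact power is 79.9%. This reproduces, and nothing below alters it.

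**2. Window.** Let P be POAF incidence over hospital plus home, and f the share of POAF patients whose AF occurs only before discharge. Section b's rule yields P(1 − f). The Background gives P = 20-50% for cardiac surgery generally, so 20 × 0.20 = 4 to 20 × 0.50 = 10 patients in an arm of 20. The documents do not give f. Over its full range of 0 to 1, the cases lost run from 0 to all 4, or from 0 to all 10.

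**3. Duration from daily tracings.** With EKGs 24 h apart and k consecutive positives from one episode, duration lies between (k − 1) × 24 and (k + 1) × 24 h.

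- k = 1: from minutes to just under 48 h.
- k = 2: 24 to 72 h, or two short episodes.

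**4. Detection.** For an EKG timed at random relative to AF, the chance that it falls in an episode of h hours is min(1, h/24), multiplied by adherence.

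| Episode | Full adherence | 80% adherence |
|---|---|---|
| 1 h | 1/24 = 4% | 3% |
| 6 h | 6/24 = 25% | 20% |
| 12 h | 12/24 = 50% | 40% |

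**5. Count.** Take the same 24 AF hours as n episodes of h hours, with positives distributed Binomial(n, h/24) under full adherence.

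| Pattern | Expected positives | P(none) | P(two or more) |
|---|---|---|---|
| 1 × 24 h | 1.0 | 0% | 0% |
| 3 × 8 h | 3 × 1/3 = 1.0 | (2/3)³ = 30% | 26% |
| 12 × 2 h | 12 × 1/12 = 1.0 | (11/12)¹² = 35% | 26% |

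A simulation of 20,000 patients, with 21 home days assumed and one fixed clock time, agreed: P(none) was 0, 0.297 and 0.349. A second set of patterns placed 72 AF hours in 28 days. As 1, 3, 6 or 36 episodes, they gave mean positives of 3.0, 2.9, 2.9 and 2.8. The number of positives does not track the number of episodes.

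**6. Denominator for telemetry burden.** The Background attributes 2 to 5 extra hospital days to POAF. For 24 AF hours, percent of monitored time is 24/((base + extra) × 24). The base stay is an assumption.

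| Base stay | No extra days | +2 days | +5 days |
|---|---|---|---|
| 4 days | 25% | 17% | 11% |
| 5 days | 20% | 14% | 10% |
| 7 days | 14% | 11% | 8% |

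A percentage alone can therefore fall because the stay lengthened.

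**The case against.** The strongest reply is that the plan never says it will compute episode count or duration from the home EKGs. The burden sentence is a data-capture statement that names no source, and it comes in a paragraph that also mentions continuous telemetry. Aim 2 lists two measures and two sources, which could be matched selectively. A reader might infer that the plan commits itself to an invalid conversion of daily tracings into episodes; the documents do not support that. What stands is narrower: Aim 2 attaches burden to both sources, section b sits under a post-discharge heading, and no text confines burden to telemetry.

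A reader might also infer that the trial will certainly discard in-hospital POAF. That too goes beyond the text, because Aim 2 includes the hospital stay. The plan contradicts itself, and only a literal use of section b causes the loss.

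Three further objections are fair:

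- Telemetry during a readmission would show onset and duration, so what should be excluded is the spot tracing, not every recording after the index stay.
- The documents say that patients are on telemetry, not that tracings are kept or AF hours extracted, so the remedy needs some work.
- A telemetry episode count also needs an episode definition, which the plan lacks.

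Finally, this is a pilot that asks only for a trend and descriptive statistics. That limits the weight of the point but does not remove it, because those statistics are what the next study will use.

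**Conclusion.** Both parts hold and should be corrected. The window conflict is the more serious, since it changes who is a case for the stated secondary aim. Its size is bounded only by the full range in step 2, because the documents do not split POAF by time of onset. The burden part is a mismatch between a definition and a measurement. That a daily tracing shows neither onset nor end rests on no numerical assumption. The detection and count figures are illustrations with hypothetical episode patterns, full adherence unless stated, and EKG times unrelated to AF.

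It would be wrong to conclude that home EKGs are of no use. They can show that AF occurred, and they contribute to yes/no incidence. Nor does the point touch the primary safety objective, the sample size, the stated power or the chi-square/Fisher comparison of incidence.

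**What to change.** 1. **Incidence window.** Change the heading and first sentence of section b so that POAF incidence runs from the end of surgery through the surgical follow-up appointment. Count any AF on telemetry or on a home EKG as POAF (yes/no), and also report it by source. Align Aim 2 with this wording.
2. **Burden.** State that episode count and duration come from continuous monitoring only: index-stay telemetry, with any readmission telemetry reported separately. Label the result in-hospital burden, state the episode definition used, and show AF hours beside monitored hours.
3. **Home data.** Report any AF (yes/no) and the numbers of EKGs that were AF-positive, recorded and due, so that missed days are visible. Derive no episode count or duration from them.

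**Cost.** The change needs revised wording, a few summary lines, and CRF items for AF hours and monitored hours, including the work of extracting them from telemetry. There will be no single burden figure across hospital and home. Because monitored time lengthens with POAF, AF hours must stand beside any percentage.
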